6.3.1 Subjects that have drug stopped for robust response

Subjects that have drug stopped for robust response or for a stable response with no significant improvement in their counts over a 6 month period will have blood counts monitored every three months be seen for up 3 years after the last dose of drug, and then be taken off study as long as the subject maintains response. Subjects off drug must be evaluated at the NIH Clinical Center every 12 months (+/- 30 days). Evaluations designated by the “***” below will only need to be completed for subjects at response assessment every 6 months. Subjects may be seen for monthly interim visits at the NIH or at their referring home health care provider. At the clinical investigator's discretion, participants may be evaluated more frequently if medically indicated based on disease status. If subjects are to be followed at home, progress notes (if available) and laboratory results from the home health care provider and laboratory must be faxed to the study research nurse.

Testing during NIH visit (every 12 months) required for patients while on extended access but off eltrombopag:

- Complete blood counts with differential (monthly +/- 7 days for 6 months off eltrombopag, then every 3 months for 3 years)
- Bone marrow aspiration and core biopsy, to be stained for standard morphologic analysis and quantitation of cellularity with hematoxylin and eosin, and special stains to assess reticulin and collagen, primitive stem and progenitor cells via CD34 immunohistochemistry, and other lineage-specific or special stains as indicated to classify any abnormalities. (every 12 months +/- 60 days for three years)
- Bone marrow chromosomal analysis via standard cytogenetic techniques (every 12 months +/- 60 days for three years)
- Flow cytometry of the peripheral blood to quantitate GPI-negative cells (every 12 months +/- 60 days for three years)
- FACT questionnaire (every 12 months +/- 60 days for three years)
- Iron panel (ferritin, transferrin, % saturation) at PI's discretion if indicated for iron metabolism and excretion studies (every 12 months +/- 60 days)
- Lymphocyte phenotyping (TBNK flow cytometry)
- Research blood as detailed in section 7
- 24 hour urine collection to determine the total iron content at PI's discretion if indicated for iron metabolism and excretion studies (every 12 months +/- 60 days)

6.4 Off study assessment

Patients who fail to respond to eltrombopag after 16 or 20 weeks (+/- 10 days) of therapy or who are taken off treatment prior to the 6 months evaluation for any of the other reasons listed in section 8.6 will likely choose to pursue other treatments, including immunosuppressive therapy, related, unrelated donor or cord blood transplantation, or experimental therapies. We will offer patients a follow-up evaluation at the NIH 6 months following being taken off eltrombopag treatment either due to lack of response or for the other reasons listed in section 8.6, but this visit will not be required. If they do not return to the NIH, we will contact their primary hematologist for information on their current hematologic status 6 months following their final dose of eltrombopag, and then take them off study.

If patients do return to the NIH at 6 months (+/- 30 days) for the off study assessment, the following may be performed, and then the patient will be taken off study:

- History and physical examination
- CBC with differential
- Acute care (Na, K, Cl, CO₂, Creatinine, Glucose, and Urea Nitrogen), Mineral (Phosphorus, Magnesium, Albumin, and Calcium), Hepatic (Alk Phosphatase, ALT, AST, Total Bilirubin, and Direct Bilirubin), and Other (Total Protein, CK, Uric Acid, and LDH) panel
- Reticulocyte count
- Peripheral blood smear
- Flow cytometry of the peripheral blood to quantitate GPI-negative cells
- Bone marrow biopsy with reticulin and collagen staining and aspiration with cytogenetics
- Lymphocyte phenotyping (TBNK flow cytometry)
- Research blood as detailed in section 7
- Iron panel (ferritin, transferrin, % saturation) at PI's discretion if indicated for iron metabolism and excretion studies
- 24 hour urine collection to determine the total iron content at PI's discretion if indicated for iron

General Quality of Life FACT questionnaire

The FACT instrument is a health assessment instrument that was originally designed to measure multi-dimensional quality of life in cancer therapy. There are several different subscales for anemia (FACT-An)¹⁰, neutropenia (FACT-N) and thrombocytopenia (FACT-Th) allowing it to be adapted for the specific use in patients with hematological disorders. There are 28 core generic questions which examine physical, social, emotional and functional well-being. The FACT will be completed at baseline and the end of the study (after 16 weeks and 20 weeks (+/- 4 days) of treatment). Subjects who leave the study prematurely will also be administered the FACT questionnaire.

7.0 ANCILLARY LABORATORY RESEARCH STUDIES

7.1 Collection of samples

During the course of participating on this study, an additional 30 cc of blood (NIH visits only) and 5 cc of bone marrow aspirate each time a patient has a bone marrow examination may be requested. These samples will be stored with the subject's permission for other exploratory laboratory research studies reviewed and approved by the IRB and listed in Appendix A. Research samples will be coded and stored in the secure laboratory of the principal investigator.

7.2 Intended use: These specimens will not be read by a pathologist or be used for diagnostic purposes. Studies will not be used in assessing the primary endpoint but will be undertaken for descriptive or

exploratory ancillary research. The following laboratory research studies may be done and if done, may be correlated with the presence or absence of response. Additional studies which are approved by the IRB and listed in the Appendix of the protocol may be done on stored samples.

- T cell receptor V-beta profile in the marrow and peripheral blood
- Extended peripheral blood flow cytometric phenotyping for cell surface or intracellular proteins
- Evaluation for the presence of abnormalities of the telomere repair complex including telomere length and genetic testing of genes associated with the telomere repair complex
- Evaluation for the presence of abnormalities of genes associated with hematopoiesis, via genetic testing or gene expression analysis
- Serum cytokine, chemokines and soluble receptor levels
- Serum (or plasma) and cells for viral analyses
- Hematopoietic progenitor colony, long term-culture-initiating cell, and immunodeficient mouse engraftment assays for primitive cell content and function
- Pharmacokinetic studies of eltrombopag kinetics performed at PI's discretion
- 24 hour urine to investigate the influence of eltrombopag on iron metabolism and renal excretion.
- In the event there is any extra sample, these will be stored with the subject's permission for other exploratory laboratory research studies reviewed and approved by the IRB and listed in Appendix A.
- Serum thrombopoietin level at baseline, weeks 16 and 20, 6 months after last dose of study drug, and if on extended access, then every 6 months NIH visits

7.3 Tracking: Samples will be ordered and tracked through the CRIS Research Screens. Should a CRIS screen not be available, the NIH form 2803-1 will be completed and will accompany the specimen and be filed in the medical record. Specimens will be entered in the NHLBI Biospecimen Inventory System (BSI). Samples will not be sent outside NIH without IRB notification and an executed MTA.

7.4 Storage: Research samples will be stored with identifiers in the secure laboratory in the Hematology Branch.

7.5 End of study procedures: Samples from consenting subjects will be stored until they are no longer of scientific value or if a subject withdraws consent for their continued use, at which time they will be destroyed.

7.6 Loss or destruction of samples: Should we become aware that a major breach in our plan for tracking and storage of samples has occurred, the IRB will be notified.

8.0 BIOSTATISTICAL CONSIDERATIONS

8.1 Objectives

The *primary objective* is to assess the safety and efficacy of the oral thrombopoietin receptor agonist (TPO-R agonist) eltrombopag in moderate aplastic anemia patients or patients with bone marrow failure and unilineage cytopenia.

Secondary objectives include the analysis of the incidence and severity of bleeding episodes, clonal evolution to PNH, clonal chromosomal population in bone marrow, myelodysplasia by morphology, or acute leukemia and the impact on quality of life.

8.2 Endpoints

The **primary endpoint** will be the portion of drug responders as defined by changes in the platelet count and/or platelet transfusion requirements or hemoglobin and/or PRBC transfusion requirements and the toxicity profile as measured using the CTCAE criteria. Treatment response for the platelet lineage is defined as an absolute increase of $\geq 20 \times 10^9/L$ above baseline at 16 or 20 weeks, measured on at least two serial measurements performed one week apart and sustained for 1 month or more without support of platelet transfusions, or for transfusion dependent patients stable platelet counts with transfusion independence for ≥ 8 weeks. For patients with anemia (untransfused hemoglobin ≤ 8.5 g/dL), a treatment response will be an increase in Hb by ≥ 1.5 g/dL at four months, measured on at least 2 serial measurements and sustained for 1 month or more without transfusion support **OR** for transfusion dependent patients, reduction of units of RCC transfused by 50%/8 weeks compared with the pretreatment transfusion number in the previous 8 weeks or transfusion independence (no transfusions for ≥ 8 weeks).

Criteria for response: Treatment response for the platelet lineage is defined as platelet count increases to 20,000/uL above baseline at 16 or 20 weeks, or freedom from platelet transfusions for ≥ 8 weeks in transfusion-dependent patients. For patients with anemia (untransfused hemoglobin ≤ 8.5 g/dL), a treatment response will be an increase in Hb by ≥ 1.5 g/dL at four months, measured on at least 2 serial measurements and sustained for 1 month or more without transfusion support **OR** for transfusion dependent patients, reduction of units of RCC transfused by 50%/8 weeks compared with the pretreatment transfusion number in the previous 8 weeks or transfusion independence (no transfusions for ≥ 8 weeks). We will analyze a composite of both lineage responses and the individual responses.

Secondary endpoints will include incidence of bleeding, changes in serum thrombopoietin level (as measured by enzyme-linked immunosorbent assay), clonal evolution to PNH, clonal chromosomal population in bone marrow, myelodysplasia by morphology, or acute leukemia and health related *General Quality of Life (FACT questionnaire)* for Subjects ages 18 and older will be completed at baseline and 16 weeks.

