3.0 STUDY DESIGN

[figure not shown]
The study is designed as a non-randomized, Phase II, dose modification study of the oral TPO-R agonist eltrombopag in moderate aplastic anemia patients or those with bone marrow failure with unilineage cytopenia. The primary endpoint is measured at 16 to 20 weeks (+/- 7 days). Subjects with evidence for a clinical response in any lineage at 16 weeks but not yet meeting full primary endpoint response criteria, and who are tolerating investigational treatment, may receive an additional 4 weeks of eltrombopag and be reassessed after 20 weeks (+/- 7 days). At that time, if they meet primary endpoint response criteria, they will be eligible to enter the extended access part of the study. If they do not meet primary endpoint response criteria, eltrombopag will be discontinued. Subjects who cannot tolerate the medication or fail to respond by 16 to 20 weeks (+/- 7 days) will go off study. Drug dose during extended access will be at the lowest dosage that maintains stable blood counts or taken off drug for robust response until they meet off study

criteria or the study is closed. If subjects are taken off drug for robust response during extended access and maintain response, they will be taken off study after 3years.

Protocol Schema prior to January 8, 2015:

Protocol Schema after January 8, 2015:

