4.0 ELIGIBILITY ASSESSMENT

4.1 Inclusion criteria

4.1.1 Current diagnosis of moderate aplastic anemia **OR** unilineage bone marrow failure disorders.

- **Moderate aplastic anemia is defined** as aplastic anemia (hypocellular bone marrow for age) with no evidence for other disease processes causing marrow failure, and depression of at least two out of three blood counts below the normal values:

- $ANC \leq 1200/mm^3$
- platelet count $\leq 70,000/mm^3$
- anemia with hemoglobin ≤ 8.5 g/dL and absolute reticulocyte count $\leq 60,000/mm^3$ in transfusion-dependent patients

but not fulfilling the criteria for severe disease defined by depression of two of the three peripheral counts:

- $ANC \leq 500/mm^3$

- platelet count $\leq 20,000/\text{mm}^3$
 - reticulocyte count $\leq 60,000/\text{mm}^3$)
 - **Unilineage bone marrow failure disorders are defined:**
 - Hemoglobin < 8.5 g/dL and reticulocyte count $< 60,000$ or red cell transfusion dependent and hypocellular to normocellular bone marrow for age with significantly reduced erythroid precursors.
 - **OR** thrombocytopenia $\leq 30,000/\text{uL}$ or platelet transfusion dependent and hypocellular to normocellular bone marrow for age with reduced megakaryocytes.
 - No evidence of viral or drug suppression of the marrow, dysplasia, or underproduction anemias secondary to B12, folate, iron or other reversible causes.
- 4.1.2 Platelet transfusion dependent is defined as the need for platelet transfusion due to platelet counts of $< 10,000$ /uL with no bleeding (prophylactic transfusion) or $< 20,000/\text{uL}$ with bleeding (therapeutic transfusion). Red cell transfusion dependent is defined as transfusion of greater than 4 units of blood in the 8 weeks prior to study entry.
- 4.1.3 Age ≥ 2 years old
- 4.1.4 Weight > 12 kg

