8.3 Sample Size

We intend to accrual a maximum of 38 subjects for this study. Because the efficacy of eltrombopag in this patient population is unknown, we would like to reject the treatment as quickly as possible with a small number of patients if the treatment is not effective. We will use the Two-Stage Minimax Design outlined in Table 1 of Simon ⁽¹⁾ with a response probability of 20% or less to terminate the treatment and the hypothesized actual response probability of 40% or more. The sample size is determined by testing the null hypothesis $H_0: p \leq 20\%$ versus the alternative $H_1: p \geq 40\%$ at a significance level of 0.05 and a power of 0.8. At the first stage, 18 subjects will be accrued and the trial will be terminated by accepting the null hypothesis if 4 or fewer subjects respond to the treatment within 16 to 20 weeks. If 5 or more subjects respond to the treatment within 16 weeks at the first stage, then an additional 15 subjects will be accrued at the second stage. If needed, the replacement of 5 drop-out subjects will bring the total number of subjects to $n=38$. The null hypothesis of $p \leq 20\%$ will be accepted (i.e., the drug will be rejected) if the total number of responders within 16 to 20 weeks is 10 or less. This sample size is calculated by the PASS power analysis and sample size software (NCSS, LLC., [name]).

Subjects who discontinue the study drug prematurely (before 16 weeks):

Platelet count measurement will be attempted even if a patient discontinues study drug. Patients who withdraw from the study for reasons other than lack of efficacy or toxicity (rendering platelet count missing) may be replaced. All other patients should be evaluable for efficacy. Based on the assumed drop-out rate of 15-20% and the goal of having 33 evaluable patients, 5 additional patients may be enrolled if needed.

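### Transfusion-based response in 8.2 can occur without drug effect: the red-cell baseline is also the selection period, the on-treatment 8 weeks are not named, and platelet dependence needs no past transfusion

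*Combined protocol and SAP*

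**What the plan says.** **Red cells.** Section 4.1.2: "Red cell transfusion dependent is defined as transfusion of greater than 4 units of blood in the 8 weeks prior to study entry". Section 8.2 then lets a dependent subject respond through a "reduction of units of RCC transfused by 50%/8 weeks compared with the pretreatment transfusion number in the previous 8 weeks", or through no transfusion for at least 8 weeks.

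**Platelets.** Section 4.1.2: "Platelet transfusion dependent is defined as the need for platelet transfusion due to platelet counts of" under 10,000/uL without bleeding, or under 20,000/uL with bleeding. It gives no number of transfusions and no look-back period. Section 8.2 states the response twice. The primary-endpoint paragraph asks for stable counts together with at least 8 weeks of independence. The criteria paragraph asks only for the count rise "or freedom from platelet transfusions for" at least 8 weeks.

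**Timing.** Section 3.0 places the assessment at 16 to 20 weeks (+/- 7 days), and 8.3 counts responders within 16 to 20 weeks. In 8.2 the time points attach to the platelet and hemoglobin rises, not to the transfusion criteria.

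**Design.** Section 3.0: "The study is designed as a non-randomized, Phase II, dose modification study of the oral TPO-R agonist eltrombopag". Section 8.3 uses a Simon two-stage minimax design "with a response probability of 20% or less to terminate the treatment and the hypothesized actual response probability of 40% or more", "at a significance level of 0.05 and a power of 0.8". It gives no derivation of the 20%.

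**The concern.** A subject who enters because one 8-week count was high is then judged against that same count. If the underlying need is stable, the next count will on average be lower, and some subjects will fall by half through regression to the mean alone. An unnamed counting period adds to this if an analyst may take the most favourable 8 weeks, and it lets two analysts count different responders from the same data. On the platelet side, a subject classed as dependent on counts, but rarely or never transfused before entry, can meet the 8-week criterion unchanged.

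Section 5.6 leaves transfusion to clinical indication, and there is no concurrent control. The 20% null rate is thus the only allowance for chance response. If chance responses pushed the overall no-effect rate above 20%, the test would no longer hold its stated level.

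**Working it through.** **1. The plan's own figure.** Inputs from 8.3: "18 subjects will be accrued and the trial will be terminated by accepting the null hypothesis if 4 or fewer subjects respond"; otherwise 15 more are accrued, and the drug is rejected at 10 or fewer of 33.

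P(pass | p) = sum over x = 5 to 18 of Bin(x; 18, p) × P(Bin(15, p) ≥ 11 − x).

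At p = 0.20 this is 0.0458 and at p = 0.40 it is 0.8011, so the design meets its stated level and power. The sample-size calculation is correct.

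**2. Red-cell reduction with no drug effect, last 8 weeks before week 16.** The documents give no transfusion rates, so the rates are assumptions. X1 (pre-entry units) and X2 (on-treatment units) are independent Poisson counts with the same mean. Selection is X1 ≥ 5, and response is X2 ≤ X1/2.

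P(response) = [sum over x ≥ 5 of P(X1 = x) × P(X2 ≤ x/2)] / P(X1 ≥ 5).

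At mean 5: 0.1535 / 0.5595 = 0.274.

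**3. Any 8-week window up to week 16.** Same assumptions, simulated daily over 112 days, taking the lowest 56-day total.

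| Mean units per 8 weeks | 4 | 5 | 6 | 8 | 10 |
|---|---|---|---|---|---|
| Last 8 weeks, 1-unit Poisson | 38% | 27% | 20% | 12.5% | 9% |
| Last 8 weeks, 1-unit, variance half the mean | 23% | 14% | 9% | 5% | 3% |
| Last 8 weeks, 2-unit Poisson episodes | 54% | 45% | 37% | 27% | 21% |
| Any 8 weeks to week 16, 1-unit Poisson | 75% | 63% | 52% | 37% | 28% |

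Two-unit episodes at more regular intervals (gamma gaps, shape 4) give 33%, 22%, 15% and 7% in the last 8 weeks at means 4, 5, 6 and 8.

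**4. Red-cell independence by chance, fixed 8 weeks.** P = exp(−mean) for 1-unit use: 1.8% at mean 4 and 0.2% at mean 6. With 2-unit episodes, exp(−mean/2): 13.5% and 5.0%. Independence is much harder to reach by chance than a 50% fall.

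**5. Platelets.** With an unchanged need of 1, 2 or 4 transfusions per 8 weeks, a transfusion-free fixed 8 weeks has probability exp(−1) = 37%, exp(−2) = 14% or exp(−4) = 2%. At 8 per 8 weeks it is below 1%. A subject with no recent transfusion can qualify with no change at all.

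**6. Effect on the trial.** From step 1, the pass probability is 4.6% at a no-effect rate of 20%, 16.6% at 25% and 37.3% at 30%. The overall rate is (share on the red-cell route × chance response) + (remaining share × their no-effect rate). Taking an assumed 10% for the rest:
- 0.5 × 20% + 0.5 × 10% = 15%: pass 0.6%.
- 0.3 × 37% + 0.7 × 10% = 18.1%: pass 2.4%.
- 0.5 × 37% + 0.5 × 10% = 23.5%: pass 12%.

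**The case against.** A reader might infer that any favourable 8 weeks is the rule as written, and take the 28–75% row as the operating rate. The documents do not support that. Section 3.0 fixes the assessment, 5.5 turns on criteria not yet met at 16 weeks, and 6.3 refers to criteria fulfilled at the 16 or 20 week visit. These point to status at the visit. The wording in 8.3 leaves the wider reading open, so the point stands as an ambiguity.

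A reader might also infer that the type I error is inflated. That is not shown. The chance rates apply only to red-cell-dependent subjects. Others are judged on a hemoglobin rise with serial and sustained measurements, or on platelet criteria, and moderate aplastic anemia can qualify on neutrophils and platelets alone. Two of the three mixes in step 6 stay below 5%.

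Means of 4 to 6 units sit at the selection threshold, where the bias is greatest. Higher or more regular need gives less, and 2-unit episodes give more, so the size is undetermined. Study entry and pretreatment may also differ by days, so the two 8-week periods are nearly, not provably, identical.

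The platelet point is limited too. One of the two wordings does require stable counts, and sections 2.3 and 2.9 describe frequent transfusion at low counts, where chance freedom is small. It concerns subjects with few or no recent transfusions.

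**Conclusion.** The point holds as a weakness in the endpoint definition. Selection and comparator share essentially the same 8 weeks, the on-treatment 8 weeks are not named, platelet dependence requires no past transfusion, and 8.2 carries two platelet wordings. In an uncontrolled trial some responses can then occur without drug effect: about 9–38% of red-cell-dependent subjects at means of 10 down to 4 units, assuming stable 1-unit Poisson need and a fixed final window. Regular 1-unit use lowers this and 2-unit episodes raise it.

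The documents do not support the stronger conclusion that the test cannot separate drug from chance. The 20% null absorbs some chance response, and the false-positive risk stays below 5% while the overall no-effect rate is under 20%. The 25% rate is hypothetical, because neither the share of subjects on this route nor their transfusion variability is given. This is worth correcting because it is cheap; it does not invalidate the design.

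**What to change.** In 8.2:
1. Count the transfusion response only in the 8 weeks ending at the week 16 assessment, or week 20 for subjects reassessed then. At a mean of 6 units this removes the gap between 52% and 20%.
2. Count platelet-transfusion freedom as response only in subjects with at least one platelet transfusion in the 8 weeks before entry, and reconcile the two platelet wordings.
3. Prespecify a supportive analysis in which red-cell response counts only transfusion independence or the hemoglobin criterion.

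A 16-week averaged baseline is not recommended as a primary change. It still contains the selection period and penalises recent worsening: 6 units in the last 8 weeks after none before gives a baseline of 3, so response would need 1 unit or fewer. It could serve as a sensitivity analysis where records exist.

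The document is a 2019 amendment to a study begun before 2015. If outcomes have already been assessed, leave the primary endpoint as it is and apply the platelet restriction as a labelled sensitivity analysis.

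The cost is a few sentences and a check of pre-entry platelet transfusion records; a few marginal responders are no longer counted. Because 6.3 refers to 8.2 for extended access, the amendment should state whether the new counting rule is for analysis only.

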Eligible patients can have treated or untreated MAA, as well as counts meeting criteria for MAA following a partial response to treatment with immunosuppression for SAA. We will also include patients with bone marrow failure and unilineage cytopenia. Treatment response for the platelet lineage is defined as platelet count increases to 20,000/uL above baseline at 16 to 20 weeks, or freedom from platelet transfusions for ≥ 8 weeks in transfusion-dependent patients. For patients with anemia (untransfused hemoglobin ≤ 8.5 g/dL), a treatment response will be an increase in Hb by ≥ 1.5 g/dl at four months, measured on at least 2 serial measurements and sustained for 1 month or more without transfusion support **OR** for transfusion dependent patients, reduction of units of RCC transfused by 50%/8 weeks compared with the pretreatment transfusion number in the previous 8 weeks or transfusion independence (no transfusions for ≥ 8 weeks). Subjects with evidence for a clinical response in any lineage at 16 weeks but not yet meeting full primary endpoint response criteria, and who are tolerating investigational treatment, may receive an additional 4 weeks of eltrombopag and be reassessed after 20 weeks. At that time, if they meet primary endpoint response criteria, they will be eligible to enter the extended access part of the study. If they do not meet primary endpoint response criteria, eltrombopag will be discontinued.

The **primary objective** is to assess the safety and efficacy of the oral thrombopoietin receptor agonist (TPO-R agonist) eltrombopag in moderate aplastic anemia patients or patients with bone marrow failure and unilineage cytopenia. **Secondary objectives** include the analysis of the incidence and severity of bleeding, clonal evolution to PNH, clonal chromosomal population in bone marrow, myelodysplasia by morphology, or acute leukemia and the impact on quality of life.

Table of Contents

1.0	OBJECTIVES	4
2.0	BACKGROUND AND SCIENTIFIC JUSTIFICATION	4
3.0	STUDY DESIGN.....	17
4.0	ELIGIBILITY ASSESSMENT.....	18
4.1	Inclusion criteria	18
4.2	Exclusion criteria	19
5.0	TREATMENT PLAN.....	20
6.0	CLINICAL MONITORING	23
7.0	ANCILLARY LABORATORY RESEARCH STUDIES	27
8.0	BIostatistical CONSIDERATIONS	28
8.1	Objectives	28
8.2	Endpoints	29
8.3	Sample Size.....	29
8.4	Statistical Methods.....	30
8.5	Stopping rules	30
8.6	Off Study Criteria	31
9	DATA AND SAFETY MONITORING	32
9.1	Data and Safety Monitoring.....	32
9.2	Event Characterization and Reporting	33

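### Section 8.2 defines platelet response in two conflicting ways, and 8.3 does not say which one is counted against the 4/18 and 10/33 boundaries

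*Combined protocol and SAP*

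**What the plan says.** Section 8.2 defines platelet response in two consecutive paragraphs.

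- **Primary-endpoint paragraph.** A rise of at least 20 x 10^9/L at week 16 or 20, "measured on at least two serial measurements performed one week apart and sustained for 1 month or more without support of platelet transfusions". Transfusion-dependent patients instead need stable counts together with at least 8 weeks of transfusion independence.
- **Criteria-for-response paragraph.** "Treatment response for the platelet lineage is defined as platelet count increases to 20,000/uL above baseline at 16 or 20 weeks", or at least 8 weeks free of platelet transfusion in transfusion-dependent patients. The count-rise limb has no repeat measurement, duration or transfusion-free condition. The transfusion limb has no stable-count condition.

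The opening summary uses the looser form: "Treatment response for the platelet lineage is defined as platelet count increases to 20,000/uL above baseline at 16 to 20 weeks". It then makes entry to extended access depend on the primary endpoint: "At that time, if they meet primary endpoint response criteria, they will be eligible to enter the extended access part of the study". Section 3.0 refers to subjects with "evidence for a clinical response in any lineage at 16 weeks but not yet meeting full primary endpoint response criteria" and does not define the full criteria there.

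Section 8.3 sets the stage 1 rule: "the trial will be terminated by accepting the null hypothesis if 4 or fewer subjects respond to the treatment within 16 to 20 weeks". The next sentence continues to stage 2 on 5 or more responses within 16 weeks, without the extension to 20. The final boundary is 10 of 33. Neither platelet rule is cited.

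On lineages, 8.2 says "We will analyze a composite of both lineage responses and the individual responses". The hemoglobin limb is limited to anemic or transfusion-dependent patients. The platelet count-rise limb has no baseline platelet condition in either paragraph, and section 5.2 expects platelets to rise in patients who enter for anemia with normal or near-normal platelet counts.

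**The concern.** A two-stage design turns one integer into a decision. If two written rules can give two integers for the same patients, the operating characteristics in 8.3 belong to neither rule until one is named. A transient or transfusion-supported rise at the week 16 or 20 visit counts under one paragraph and not under the other.

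The study is single-arm, and section 9.1 has the principal investigator monitoring efficacy data. A rule chosen once counts are visible would be post hoc. The stage 1 decision has a further ambiguity: a subject who first responds between weeks 16 and 20 counts in the stopping statement but not in the continuing one.

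**Working it through.** **1. Reproduce the design.** Inputs from 8.3: null rate 20%, alternative 40%, level 0.05, power 0.80, boundaries 4/18 and 10/33. Let X1 ~ Bin(18, p) and X2 ~ Bin(15, p). Then

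P(declare active) = sum over x = 5 to 18 of P(X1 = x) × P(X2 ≥ 11 − x).

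This gives 4.58% at p = 0.20 and 80.11% at p = 0.40. A search over all two-stage designs confirms 33 as the smallest feasible total, with 4/18 and 10/33 having the lowest expected size at that total. The sample-size arithmetic is correct.

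**2. When would one extra counted responder change the final verdict?** There are two routes:

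- A: exactly 4 of 18, followed by at least 6 of 15. The extra subject must be in stage 1.
- B: stage 1 passed and exactly 10 of 33 in total. The extra subject may be in either stage.

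A = P(X1 = 4) × P(X2 ≥ 6); B = sum over x = 5 to 10 of P(X1 = x) × P(X2 = 10 − x).

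| True rate | A | B | Extra subject in stage 1 (A + B) | Extra subject in stage 2 (B) |
|---|---|---|---|---|
| 20% | 21.53% × 6.11% = 1.31% | 4.29% | 5.6% | 4.3% |
| 30% | 16.81% × 27.84% = 4.68% | 11.46% | 16.1% | 11.5% |
| 40% | 6.14% × 59.68% = 3.66% | 5.87% | 9.5% | 5.9% |

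These are chances that one such subject would matter, not that one exists. The first factor in A is also the chance of sitting exactly on the stop-or-continue boundary.

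**3. Illustration under assumed disagreement.** The documents give no rate at which the rules differ. Suppose the strict rate is 20% and a share e of strict non-responders is also counted under the looser rule. The counted rate is 0.20 + 0.80e, and the expected extra subjects are 33 × 0.80 × e.

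| e (assumed) | Counted rate | Extra subjects of 33 | P(declare active) |
|---|---|---|---|
| 0 | 20.0% | 0 | 4.6% |
| 2% | 21.6% | 0.5 | 7.4% |
| 5% | 24.0% | 1.3 | 13.4% |
| 10% | 28.0% | 2.6 | 28.2% |

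Every strict responder also meets the looser rule, so the chance that the two rules give different verdicts on the same patients is the difference from the e = 0 row: 2.8, 8.8 and 23.6 points.

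**4. The other direction.** If the 40% was set with the looser rule in mind and 5% or 10% of looser responders fail the strict rule, the strict rate is 0.40 × 0.95 = 38% or 0.40 × 0.90 = 36%. Power is then 73.3% or 65.3%.

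**The case against.** The best defence is that the documents already point to the stricter rule. It stands in the paragraph that states the primary endpoint, and 8.3 counts responders, the term that paragraph uses. A four-week extension for subjects not yet meeting the full criteria also fits a rule that needs a sustained month better than a single-visit rule. On this view the criteria paragraph is shorthand.

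Much of that stands, and it is why the stricter rule is the one to name. It does not settle the matter. The criteria paragraph repeats the confirmation and one-month wording in full for hemoglobin and omits it only for platelets, and the opening summary does the same. Section 6.3 refers to 8.2 for the response criteria, and 8.2 contains both rules.

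Four stronger readings are tempting and are not supported:

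- **That the looser rule has no duration or transfusion condition at all.** It has one in its transfusion-freedom limb. The gap is in the count-rise limb, plus the missing stable-count condition.
- **That the missing baseline platelet condition is an error.** It is the same in both paragraphs, so it is a design choice for a platelet-or-hemoglobin composite, and the individual lineages will be reported. It merits a sensitivity count, not a change to the endpoint.
- **That the trial's error rate is 13% or 28%.** Those figures depend entirely on an assumed disagreement rate.
- **That the rule was, or will be, chosen on results.** Nothing shows this. Section 9.1 also provides for data and safety monitoring board review every 6 to 12 months, with scope to recommend stopping for efficacy considerations.

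**Conclusion.** The point holds as an ambiguity in the primary count that should be fixed; it is not a flaw in the design or its sample size. Two conflicting platelet definitions stand in 8.2, 8.3 names neither, and the stage 1 window is stated in two ways. Its size is conditional. With one discordant subject, the chance that the final verdict turns on that subject is about 4% to 16%, depending on the true rate (20% to 40%) and the stage. This rests on independent subjects with a common response rate and no other disputed responders. The number of discordant subjects cannot be derived from the documents.

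**What to change.** For the statistical count only, in section 8.3:

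1. Name the primary-endpoint paragraph's platelet rule, both limbs, as the one counted at both stages and as the rule to which the 20% and 40% rates refer.
2. Use a single response window in the two stage 1 statements.
3. State whether the sustained month may run past the week 16 or 20 visit.
4. Report the count under the looser rule as a sensitivity analysis.
5. As a further sensitivity count, leaving the primary endpoint as it is, report the number of responders after excluding those credited only through a platelet rise whose platelet lineage did not meet an entry criterion in 4.1.1.
6. If outcomes are already known, report both counts and the date on which the rule was chosen. This may apply: the text is a 2019 amendment, and section 5.1 mentions enrolment in the past tense.

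The cost is wording and two extra counts; N and the boundaries are unchanged. The reported response rate may be lower, and power falls if the 40% was set with the looser rule in mind.

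The same definitions also govern stopping drug and extended access (opening summary, 3.0, 5.5, 6.3). The blood-count schedule conflicts as well: weekly in one part of 6.2, every two weeks in another part and in Appendix B. The sponsor must reconcile those passages; no clinical rule is proposed here.
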